**LIST OF ABBREVIATIONS**

AUDIT	The Alcohol Use Disorders Identification Test
AERP	atrial effective refractory period
AF	atrial fibrillation
BAC	blood alcohol concentration
BrAC	breath alcohol concentration
CHADS 2	stroke risk index: Cardiac Failure, Hypertension, Age, Diabetes, Stroke [Doubled]
CRF	case report form
CS	coronary sinus
CT	computed tomography
EC	Ethics Committee
ECG	electrocardiogram
PAC	premature atrial contraction
PV	pulmonary vein
TEE	transesophageal echocardiogram
TIA	transient ischemic attack
TTE	transthoracic echocardiogram
SAE	serious adverse event
UCSF	University of California, San Francisco

## 1.0 BACKGROUND

Atrial Fibrillation (AF), the most common sustained arrhythmia in the United States, has profound public health implications: the lifetime risk of AF is 1 in 4, the disease affects several million Americans, and it is the most common cause of embolic stroke. Unfortunately, the pathogenesis of AF is still poorly understood and has multiple influences, with ethanol likely being one of particular importance. Ethanol is the most commonly consumed drug in the United States. In the 2001 US National Household Survey on Drug Abuse, 84% of people surveyed above the age of 12 admitted to having consumed ethanol in the past, with a quarter of men, and nearly a fifth of women, admitting to at least one episode of binge ethanol drinking (>5 drinks in a single sitting) during the previous month. The mechanism(s) by which ethanol increases the risk for AF, or “triggers” AF in certain individuals are unknown.

The widest body of literature is epidemiological, and those studies have suggested an association between ethanol use and the risk for AF since the initial cases of “holiday heart” were described in the 1970s. The patients in the initial case reports were generally male, middle-aged or younger chronic alcoholics who were without structural heart disease. The temporal association of acute onset paroxysmal AF with ethanol binges, in patients with otherwise normal hearts, led to the premise that AF paroxysms could be related to ethanol use. This premise was brought into question when large epidemiologic studies, such as the Framingham Heart Study, the Manitoba Follow-up Study, and the Renfrew/Paisley study, found no association between chronic ethanol use and AF. Later studies, such as the Copenhagen Heart Study and a reanalysis of the Framingham cohort, demonstrated that when controlled for the quantity of ethanol consumed and sex, an association with chronic and paroxysmal AF was seen with moderate to heavy ethanol use (>3 drinks per day) in men. From these studies it is apparent that the effect of ethanol is both multifactorial and complex. The case series and anecdotal evidence suggest that acute ethanol bingeing can induce temporary paroxysms of AF in younger patients without structural heart changes (consistent with acute electrophysiologic changes), while the epidemiological evidence suggests that chronic moderate to heavy ethanol use in men is associated with more chronic AF (consistent with a structural effect on the atria). It is unclear if these two conditions are part of continuum of risk or if they represent the diverse effects that ethanol may have on different patient populations. In order to investigate the mechanistic relationship between acute ethanol use and AF, we will perform a study of the acute electrical effects of ethanol in a non-alcoholic patient population with baseline paroxysmal AF.

### 1.1 Previous Study Data

The prevailing theory is that a PAC triggers AF, representing multiple, partially-reentrant wavelets. As experiments have been limited to animal models, a few small comparative observational (not experimental) studies in humans, and mechanistic concepts inferred by the success of certain ablation procedures, there is no human experimental model for in vivo atrial EP changes in AF. The data suggest that three readily measurable EP properties are important in the initiation and perpetuation of AF: automaticity, the effective refractory period (ERP), also reflected in the action potential duration (APD), and conduction velocity.

The changing nature of ERP (or APD) relative to the previous diastolic interval, a property called restitution, may be critical to the initiation of fibrillation. There is some evidence that when the restitution curve becomes steep (>1), meaning that the ERP (or APD) shortens disproportionate to the diastolic interval, susceptibility to fibrillation is particularly enhanced. No human study has demonstrated a causal relationship wherein a change in restitution leads to a greater propensity to AF. In isolated animal myocardial tissue preparations, ethanol consistently reduces APD.

Intracoronary ethanol prolongs ventricular conduction times in canine models.

Small (n<15) case series describing invasive EP studies before and after oral ethanol in humans were performed decades ago. The following was observed: in 10 habitual drinkers, oral whiskey resulted in a decrease in the atrial ERP that did not reach statistical significance; atrial arrhythmias could be induced with atrial extra stimulus pacing in 5 after, but not before, drinking whiskey. In 14 patients, whiskey resulted in an increase in atrial conduction time and a decrease in the ventricular ERP. And in 14 patients, whiskey resulted in the His-Purkinje system delay, and sustained atrial arrhythmias could be induced in 4 of them. Our prior study of 48 consecutive patients undergoing a standard questionnaire and right atrial ERP measurements during invasive EP studies found that greater average ethanol intake was associated with a shorter right atrial ERP.

## **2.0 INVESTIGATION PLAN**

### **2.1 Study Design**

This study is a randomized single-center single-blinded placebo controlled trial of patients age 21-90 with paroxysmal atrial fibrillation. This study will be conducted at University of California, San Francisco (UCSF) Medical Center. One hundred patients will be enrolled and will receive the study infusion (alcohol or placebo infusion).

### **2.2 Randomization and Treatment Groups**

Participants will be allocated (1:1) to a study assignment, using alternating blocked randomization (in blocks of five). Participants will be assigned to either the Ethanol Infusion group or to the Placebo Infusion group.

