### **2.3 Blinding**

To preserve blinding to infusion assignment, as much as possible, the following individuals will be blinded, during the trial:

- Study participants

- UCSF Electrophysiology team, including the electrophysiologist, electrophysiology fellow, and nursing staff during the procedure\* (not including the individuals noted below)

It will be necessary for the following individuals to be unblinded to individual participant randomization assignments only, during the trial:

- UCSF Study Coordinator(s) that administers the infusion, records the infusion assignment in the database, and oversees the infusion process during the procedure
- UCSF Anesthesia team
- UCSF Pharmacy team that prepares the study infusion

Only the following individuals will be unblinded to both individual and grouped participant randomization assignments, during the trial:

- UCSF Coordinating Center Epidemiologist that is the DSMB liaison
- UCSF Coordinating Center Analyst and Statistician that performs analyses for the DSMB reports and interim analysis

\* *NOTE: Breath alcohol readings will be taken during the study procedure for both the alcohol and placebo group participants, to help maintain blinding. Treatment group assignment will not be indicated on the infusion bags.*

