### 5.1 Screening for Inclusion/Exclusion Criteria & Randomization

Each potential participant's medical record will be reviewed for available inclusion and exclusion criteria data. After the participant provides informed consent, his or her medical history and additional demographic data will be obtained. Initial screening will occur at least 1 day prior to the patient's scheduled ablation procedure.

The pharmacy that prepares the ethanol/placebo infusion bags requires notification of the treatment assignment 1 business day prior to administration in order to prepare the infusion bag. Therefore, participants must be consented and randomized at least 1 day prior to the scheduled procedure.

Baseline measures will include:

- Inclusion/Exclusion criteria assessment
- Demographics and medical history
- World Health Organization AUDIT questionnaire
- CARDIA alcohol use questionnaire (shortened version)
- Vital signs
- Infusion, procedure, BrAC, and EP study measurements
- Arrhythmia episodes pre/during/post-procedure
- Adverse event assessment

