The HOLIDAY (HOw ALcohol InDuces Atrial TachYarrhythmias) Study

NCT Number: NCT01996943

Document Type: Statistical Analysis Plan

Document Date: 12/7/2020

HOLIDAY Study Statistical Analysis

Normally distributed continuous variables are presented as means \pm SD and were compared using t-tests, and continuous variables with skewed distributions are presented as medians and interquartile ranges (IQR) and were compared using Wilcoxon rank sum or signed rank tests as appropriate. Categorical variables were compared using chi squared and Fisher's exact tests. The proportion of atrial effective refractory periods that decreased with the infusion, the proportion of conduction times that decreased with the infusion, and the continuous change in each individual atrial effective refractory period and conduction time were assessed. Linear mixed models (LMMs) to estimate average and site-specific effects on pre- to post-infusion changes in AERP and conduction times were performed, with site and baseline values modeled as fixed effects and participants as random effects; analyses were repeated after adjusting for covariates statistically significantly different between alcohol and placebo groups. Heterogeneous relationships between pulmonary vein and non-pulmonary vein sites were assessed using formal tests for interaction. In addition, given evidence of potential effect modification by biological sex (19), tests for interaction by sex on the relationships between randomization assignment and outcomes were performed. Based on a review of repeat AERP measurements in 30 AF patients at 600 ms drive cycle length prior to the trial (yielding an average ERP of 230 ms \pm 20 ms), we estimated that 22 patients in each group would provide 90% power to detect a statistically significant one standard deviation difference in the overall AERP using a single interim analysis for efficacy (assessed by an independent Data Safety Monitoring Board) and an overall two-sided $\alpha = 0.05$. We based power calculations for the secondary analysis on 25 paroxysmal AF patients in whom AF induction occurred in 20%; we therefore estimated that 50 patients in each group would provide 84% power to detect a 30% increase in AF induction (20% versus 50%) with ethanol, again using a single interim analysis for efficacy and an overall two-sided $\alpha = 0.05$. Analyses were conducted using Stata version 16 (College Station, Texas). Two-sided p values < 0.05 were considered statistically significant.

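### Blocks of five cannot be 1:1, the alternation is undefined, and staff who know earlier assignments are not kept out of screening, so part of the sequence can be predicted

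*Protocol*

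**What the plan says.** Protocol 2.2 states the ratio, "Participants will be allocated (1:1) to a study assignment", and the method, "using alternating blocked randomization (in blocks of five"). It does not define the alternation, and it does not say who generates or holds the list. Section 2.1 gives the setting, "This study is a randomized single-center single-blinded placebo controlled trial", and the size: "One hundred patients will be enrolled and will receive the study infusion". The SAP's power statement for AF induction assumes equal arms: "50 patients in each group would provide 84% power".

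Section 2.3 names those who know assignments during the trial. Among them is the "UCSF Study Coordinator(s) that administers the infusion, records the infusion assignment in the database, and oversees the infusion process during the procedure". This person or these people are "unblinded to individual participant randomization assignments only, during the trial"; only Coordinating Center staff also see grouped assignments. Section 5.1 sets the timing: "participants must be consented and randomized at least 1 day prior to the scheduled procedure". Section 2.4 (Study Visits and Windows) has consent taken, and the alcohol questionnaires given, by an unspecified member of the research team. No section describes how the next assignment is concealed, or separates those who know past assignments from those who screen, consent or schedule.

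**The concern.** Blocking limits imbalance by making each assignment depend on the ones before it. The cost is that someone who knows the past assignments and the rule can foresee some of the future ones. A small, single, published block size raises that cost, and a fixed alternation of block composition raises it again.

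Foreknowledge does harm before randomization, when someone decides whom to approach, when to book them and whether a doubtful patient is eligible. Some of those decisions here involve judgement. Exclusion 1 rests on history, the AUDIT questionnaire or chart review, and exclusion 9 (severe intolerance to alcohol) has no threshold. If such judgements follow the expected arm, the arms differ systematically at entry. For AF induction the analysis has limited means of repair, because induction is tested only after the infusion. There is no pre-infusion value to adjust for, and the logistic regression in section 10.0 can handle only measured confounders.

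**Working it through.** **Inputs.** Ratio 1:1 and block size five (Protocol 2.2); 100 patients (2.1); 50 per group (SAP). One running sequence is assumed, because there is one centre and no stratification factor is stated.

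**The plan's own figure.** 100 / 5 = 20 blocks. If they alternate 3:2 and 2:3, each arm gets 10 × 3 + 10 × 2 = 50. If whole blocks alternate between arms, each arm gets 10 × 5 = 50. So 50:50 overall can be reached, although no single block is 1:1.

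**Predictability.** Take an observer who knows the rule and every earlier assignment. Count (a) assignments that are certain in advance and (b) the probability that the best guess, the arm more likely to come next, is right.

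*Reading A: blocks alternate 3:2 and 2:3, with random order inside each.* The observer knows which arm has three. There are C(5,2) = 10 equally likely orders.

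| Position | Certain | Best guess right |
|---|---|---|
| 1 | 0 | 3/5 = 0.6 |
| 2 | 0 | 0.6 × 1/2 + 0.4 × 3/4 = 0.6 |
| 3 | 1/10 (both minority places used) | 0.9 × 2/3 + 0.1 × 1 = 0.7 |
| 4 | (1 + 3)/10 = 0.4 (one arm used up) | 0.4 × 1 + 0.6 × 1/2 = 0.7 |
| 5 | 1 | 1 |
| Sum | 1.5 of 5 = 30% | 3.6 of 5 = 72% |

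Over 20 blocks that is 30 certain and 72 correctly guessed of 100.

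*Reading B: each block is 3:2 or 2:3 at random and the observer is not told which.* There are 20 equally likely orders. Certain: 0.1 at position 4 and 0.4 at position 5, so 0.5 of 5 = 10%. Best guess: 0.5 + 0.6 + 0.6 + 0.7 + 0.7 = 3.1 of 5 = 62%. Here 1:1 holds only on average.

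*Reading C: whole blocks of five alternate between arms.* Once the pattern is known, only the first assignment is open, so about 99 of 100 are known.

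**Comparison.** An unrestricted list gives 0% certain and 50% guessed. For even blocks of varied size, the next table gives simulated trials of 100 in which the observer knows the set of sizes but not which one is in use. The sizes are illustrative.

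| Block sizes | Certain | Best guess right |
|---|---|---|
| 4, 6 | 6% | 69% |
| 4, 6, 8 | 2% | 68% |
| 6, 8, 10 | 2% | 66% |
| 10, 20 | 4% | 63% |

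Varied blocks remove most of the certainty but leave much of the guessing advantage.

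**The case against.** A reader might infer that the team that screens, consents and decides to go ahead can foresee the allocations. The documents do not support that.

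- No section says that the unblinded coordinator screens or consents. The inference has some basis: the follow-up call is given to the research team in 2.4 and to the Study Coordinator in 5.2, so the labels overlap. It remains an inference.
- Nor do the documents say that one coordinator knows every earlier assignment. There may be several, and 2.3 limits them to individual assignments.
- For a patient who arrives in AF, the attending decides whether to proceed (4.1), and 2.3 lists the electrophysiologist as blinded. The assignment is fixed by then, so any influence would come from disclosure and not from predicting the block. That decision is outside this point.

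Three further objections have weight. First, the 30% belongs to one of three readings. Second, foresight at consent requires that patients are randomized in the order in which they consent. Consent may be taken at a CT visit or another earlier appointment, so the next place on the list need not go to the next person approached. The figures are therefore upper limits. Third, no bias in an endpoint is shown. The AERP analysis uses within-patient change with the baseline value in the model, which limits the effect of selection on baseline AERP.

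The Operations Manual may also describe how the list is kept. Sections 2.2 and 2.3 do not refer to it for this, and it would not undo a block size that the protocol discloses.

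**Conclusion.** The point holds in this form: section 2.2 states a rule that does not fit its own ratio within a block and leaves its key term undefined. On every reading examined, someone who knows the earlier assignments can predict more of the sequence than under simple randomization. The range is 10% to about 99% certain and 62% to about 99% guessable, with 30% and 72% if blocks alternate 3:2 and 2:3. This assumes one sequence, knowledge of all earlier assignments and knowledge of the randomization order. The protocol unblinds staff who could hold much of that knowledge and states no barrier between them and recruitment. It does not show that they recruit, or that selection occurred. This should be corrected, but it does not by itself invalidate the comparison.

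**What to change.** In 2.2, replace the scheme with a computer-generated list built from even blocks of randomly varied, undisclosed size, or with an unrestricted list. State that the pharmacy or the Coordinating Center holds it and releases one assignment at a time, after eligibility and consent are recorded. This is compatible with the pharmacy's need for one business day's notice.

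In 2.3, state that staff who know earlier assignments do not screen, consent or schedule participants. Changing the blocks alone still leaves about 62% to 69% of assignments guessable by someone with that knowledge.

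The cost is a new list, a few sentences and a division of duties among coordinators. Arm sizes may differ slightly. Under a binomial(100, 0.5) model, an unrestricted list falls within 45:55 about 73% of the time and within 40:60 about 96% of the time. Even at 40:60 the efficiency relative to 50:50 is 4 × 0.4 × 0.6 = 0.96, so the power loss is negligible. Nothing here changes when the anesthesia team learns the assignment; section 7.2.1 has the anesthesiologist unblinded for safety monitoring.

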### **2.3 Blinding**

To preserve blinding to infusion assignment, as much as possible, the following individuals will be blinded, during the trial:

- Study participants

- UCSF Electrophysiology team, including the electrophysiologist, electrophysiology fellow, and nursing staff during the procedure\* (not including the individuals noted below)

It will be necessary for the following individuals to be unblinded to individual participant randomization assignments only, during the trial:

- UCSF Study Coordinator(s) that administers the infusion, records the infusion assignment in the database, and oversees the infusion process during the procedure
- UCSF Anesthesia team
- UCSF Pharmacy team that prepares the study infusion

Only the following individuals will be unblinded to both individual and grouped participant randomization assignments, during the trial:

- UCSF Coordinating Center Epidemiologist that is the DSMB liaison
- UCSF Coordinating Center Analyst and Statistician that performs analyses for the DSMB reports and interim analysis

\* *NOTE: Breath alcohol readings will be taken during the study procedure for both the alcohol and placebo group participants, to help maintain blinding. Treatment group assignment will not be indicated on the infusion bags.*

## 2.4 Study Visits and Windows

After screening and eligibility has been determined, interested participants will be consented at either their pre-procedure, standard of care CT scan, or another pre-procedure appointment at UCSF Medical Center. At this point, questionnaires addressing alcohol consumption, triggers of AF, and medical history will be administered by the research team member performing the consent process. See Figure 1 for study flow.

[figure not shown]
Safety follow-up will be performed by chart review at 3 months, 6 months, and 12 months post-procedure, when AF ablation patients normally return to clinic. If participants have no scheduled clinic appointment within the visit window (+/- 30 days for 3 and 6 months, + 6 months and - 30 days for 12 month), a member of the research team will attempt to contact the participant by phone to gather follow-up information. The clinical site will make every possible effort to ensure that each study visit is conducted within the specified window.

**Table 1. Visit Windows**

Study Visit	Scheduled Timepoint	Visit Window
Screening and Enrollment		
V0	Randomization and Procedure	
V1	Month 3*	+/- 30 days
V2	Month 6*	+/- 30 days
V3	Month 12*	+6 months/- 30 days

\**Follow-up visits will be calculated from the date of ablation procedure (i.e., baseline).*

**Figure 1. Study Flow Diagram**

\* The

*pharmacy that prepares the ethanol/placebo requires notification of the treatment assignment 1 business day prior to administration, therefore, participants must be consented and randomized at least 1 day prior to the scheduled procedure.*

## 2.5 Study Objective and Aims

The objective of this trial is to seek to reveal the mechanisms underlying the relationship between ethanol, the most commonly consumed drug in the world, and atrial fibrillation (AF), the most common arrhythmia. Specifically, we seek to determine the electrophysiological effects of acute ethanol exposure on atrial myocardium via a randomized trial of intravenous ethanol versus placebo in paroxysmal AF patients.

### Study Aims:

1. To assess the acute effects of intravenous ethanol administration on the atrial effective refractory period (AERP) and atrial conduction velocity of *in vivo* human atrial myocardium.

*Hypothesis: Intravenous administration of ethanol decreases AERP and atrial conduction velocity.*

2. To assess the acute effects of intravenous ethanol administration on the inducibility of AF of *in vivo* human atria.

*Hypothesis: Intravenous administration of ethanol increases in vivo susceptibility to AF.*

## 2.6 Inclusion/Exclusion Criteria

### 2.6.1 Inclusion Criteria

1. Aged 21-90
2. History of paroxysmal or persistent atrial fibrillation (AF)
3. Planned procedure pulmonary vein isolation (PVI) or electrophysiology study (EPS)
4. Presenting in sinus rhythm or atrial fibrillation of recent onset (the latter confirmed by sinus rhythm documented no more than one week prior)

### 2.6.2 Exclusion Criteria

1. History of substance abuse or alcoholism (determined by history, Alcohol Use Disorders Identification Test (AUDIT) questionnaire, or chart review)
